3.5.3 Exploratory Endpoint

Survival over 1 year in the ITT population. We will use the date of informed consent as the first day in the trial. Or those alive, follow-up time will be censored at the time of loss to follow-up or at the time of completion of the study.

3 PATIENT DISPOSITION

Patient disposition will be summarized for the ITT population with counts and percentages for all patients and will include the following:

- Patient who completed study (enrollment to 1 year follow-up).
- Evaluable patients (patients for whom FACT-Hep baseline to 3 months change score can be calculated).
- Patients who underwent liver transplantation or hospice transfer prior to the 3 month end point assessment.
- Patients who discontinued the study and reasons for study discontinuation.

4 DEMOGRAPHICS AND BASELINE CHARACTERISTICS

4.1 Demographics

Patient and caregiver demographics will be summarized separately for both ITT and mITT populations. Demographics will be summarized as mean (SD), median (25, 75 percentiles), min

and max for continuous and counts (percentages) for categorical variables. Demographics will include age, sex, race, ethnicity, education level, employment status, marital status, insurance status, smoking status, height, weight and BMI (Body Mass Index)

4.2 General Medical History

Medical history will be summarized as counts (percentages) for the patients and caregivers in both ITT and mITT populations. Medical history will be presented by the diseases pre-specified in the eCRF.

4.3 Current Liver Conditions

Current liver conditions pre-specified on the appropriate eCRF will be summarized as counts (percentages) for the patients in both ITT and mITT populations.

5 EFFICACY ANALYSES

5.1 Primary Efficacy Analyses

The primary analysis will be performed on the mITT population. To account for the cluster-based randomization we will utilize linear mixed model with the treatment arm indicator (binary variable) as a fixed effect and center (cluster) as the random effect. We will also adjust for the baseline FACT-Hep total score and the binary randomization strata variable (VA vs. non-VA). Namely we will consider the model $Y_{ij} = \beta_0 + \beta_1 \text{Treatment} + \beta_2 \text{Baseline FACTHep} + \beta_3 \text{Stratum} + a_j + e_{ij}$ where response Y_{ij} is change in FACT-Hep total score from baseline to 3 months for the i-th patient in the j-th center ($j=1,2,\dots,19$). The random effect of center j is $s_j \sim N(0, \sigma_s^2)$ and is assumed to be independent from random errors $e_{ij} \sim N(0, \sigma_e^2)$. Binary variable "Treatment" is coded as 1 for the hepatologist led PC and 0 for the Consultative PC. Binary variable "Stratum" is coded 1 for VA and 0 for non-VA.

The superiority null hypothesis is $H_0: \beta_1=0$ and alternative hypothesis $H_1: \beta_1 \neq 0$. We will reject the null hypothesis if two-sided P-value is < 0.05 and conclude that treatment has significant effect on change in FACT-Hep total score.

Only if superiority is not demonstrated (i.e., when superiority p-value ≥ 0.05) then the non-inferiority (NI) analysis will be performed. Non-inferiority of Model 2 (Hepatologist led PC) will be demonstrated if the lower two-sided 95% CI limit (L) for β will be greater than negative pre-specified DELTA margin, i.e., when $L > -4.0$.

In addition to the statistical hypothesis testing, 95% confidence intervals descriptively summarizing the difference in outcome between the two treatment arms, as well as outcome in each randomized arm will be computed.

A complete case analysis will be performed if the primary analysis has $\leq 10\%$ of patients with missing outcome information. If there are more than 10% of patients with missing outcome information, we will utilize multiple imputations (MI) (see section 12.4 for more details). Variables used in multiple imputations will include FACT-Hep total score values measured at baseline, 1 month, 2 months, and 3 months as well as treatment assignment, stratum variable (VA vs. Non-VA), and baseline demographics (including age, gender, education level, employment status, marital status, and smoking status). Change in FACT-Hep total score will be computed with baseline and 3 month FACT-Hep total score values resulting from MI.

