2.3 Sample Size Determination and Statistical Power

2.3.1. Sample Size Determination

Patient-reported quality of life, as measured by FACT-Hep total score, is the primary outcome measure in this study. Published estimates show the average performance on this measure for typical patients with ESLD is 143.0 points (SD 20.6) and a difference of 9 points on this measure reflects a minimal clinically meaningful difference (MCID) in QOL [1,2]. However, the power estimates below are based on SD=19.1 for change in FACT-Hep total score from baseline to 3 months observed in the study at the time of sample size re-computation (**n=936**). Patient level data analysis will be considered with adjustment for clustering, i.e., adjustment for correlation of patients' outcomes within a cluster (site). This correlation is quantified by the intraclass correlation coefficient (ICC). At the time of sample size re-computation ICC=0.09 was noted in the study.

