12.4 Handling of Missing Data

Every effort will be made to minimize the extent of missing values by proactive strategies, inevitably we will need to deal with some missing value problems [3]. To prevent and limit

missing data other than due to patient's death or curative therapy prior to completion of the study we will perform data checks and consistency checks during the study and collaborate with sites to complete missing or incorrect data items. If \leq up to 10% of patients have missing data for a particular analysis, we will conduct complete case analysis utilizing only non-missing data. However, if more missing data ($> 10\%$) is present we will utilize multiple imputations (MI) to mitigate potential bias of the complete case analysis and appropriately reflect the uncertainty due to imputations [4]. The MI method assumes that the data are missing at random (MAR), meaning that the probability of missingness depends on observed data but not on unobserved data. An imputation model will be constructed including all variables that are part of the analysis model and additional auxiliary variables (including age, gender, education level, employment status, marital status, and smoking status) that may be predictive of the missingness. Both continuous and categorical variables will be included. Multiple imputation will be performed using the PROC MI procedure in SAS 9.4 utilizing fully conditional specification (FCS) method for data sets with arbitrary missing patterns [5]. A total of 1000 imputations will be performed. Each of the imputed datasets will be analyzed separately, and the results will be combined using SAS PROC MIANALYZE to obtain valid statistical inferences that reflect the uncertainty due to imputations of missing data and account for the variability both within and between the imputed datasets.

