Study Intervention Visits (for Both Model 1 and 2)	
All patient-caregiver dyads will receive the intervention at the initial visit, and at 1, 2, and 3 months from the initial visit. Initial/ 1st visit will occur within 6 weeks after informed consent. Ascertainment of baseline assessments will occur within 1 week before the scheduled initial visit. Informed consent, baseline assessments and initial visit may occur on the same day, but must follow this sequence.
 
1, 2 and 3 month visits can occur within a window period of 1 week (before/after) of their respective times from the initial visit. All study visits can occur in person, or remotely (by phone or telehealth with the institutional secure platform).
 
All caregiver visits can occur in person or by phone, as preferred by the caregivers. The initial caregiver visit can occur on the same day or within 1 week of patient's initial visit.

Data Collection for Study Visits (Month 1, 2 and 3)	All data collection (patients and caregivers) can occur by phone, paper forms or using online surveys. ESAS, DT and PHQ-9 are conducted before the study visit (within 1 week of visit), and all other assessments are conducted after the study visit (within 1 week after the study intervention visit)
Data Collection during Follow Up	Study follow up data collection will be conducted at 6, 9 and 12 months, by phone, paper or online, within 1 week/ 7 days (before/after) of the due date.
Number of Patient Caregiver dyads	936 patients with a caregiver when available (n=563) will be enrolled. We aim to recruit approximately an equal number of patients from each of the centers. The study will have power (83.2%) for the primary analysis to detect a minimally clinically important difference of 9 points in QOL change (baseline to 3 months) between the two randomized arms.
Number of Sites	19 Clinical Centers (8 VA and 11 non-VA Academic Centers).

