**Table 2: Schedule of Assessments**

		Baseline*	Initial**	1 M	2M	3 M	6 M	9 M	12 M	Early Termination 
Informed Consent	X									
Inclusion/Exclusion Criteria	X									
Demographics (Patients & Caregivers)	X									
Medical History (Patients & Caregivers)			X			X				X 
ECOG score (Patients)			X	X	X	X				X 
Concomitant Medications (Patients)			X	X	X	X				X 
Study Intervention (Patients & Caregivers)		X	X	X	X					X 
FACT-Hep	X		X	X	X	X	X	X	X	X
ESAS	X		X	X	X	X	X	X	X	X
PHQ-9	X		X	X	X	X	X	X	X	X
Distress Thermometer	X		X	X	X	X	X	X	X	X
FAMCARE-P 13	X		X		X	X	X	X	X	X
PROMIS-29 (Patients & Caregivers)	X				X	X	X	X	X	X
MELD Labs (+/- 4 weeks for each time point) (Patients)	X 				X	X	X	X	X	X
CTP score (Patients)	X				X	X	X	X	X	X
Goal Concordant Care questionnaire (Patients & Caregivers)	X				X	X	X	X	X	X
Caregiver Burden (Zarit Burden-12)	X		X		X	X	X	X	X	X
Patient/ Caregiver Interviews***					X					
AUDIT-C and AUDIT****	X				X					X 
Healthcare Utilization	X	X	X	X	X	X	X	X	X	X
*Baseline assessments will occur by phone, online or on paper forms after informed consent, WITHIN 1 WEEK before the scheduled INITIAL VISIT. **Initial Visit must occur within 6 weeks after informed consent is provided.										
***Patient/ Caregiver Interviews will occur within 3months after the 3 month intervention, and applies only to those who opt in at the time of consent, and are selected for interviews.										

**1-, 2- and 3-month visit can occur within a window of +/- 1 week. All follow up visits (6, 9 and 12 month) can occur within a window of +/- 1 week (7 days). 1 month= 30 days**

**\*\*\*\*AUDIT-C will be administered to all patients at baseline. If the AUDIT-C score is >=4 for men or >=3 for women, the full AUDIT assessment will be completed. Only patients who take the AUDIT at baseline are required to take the AUDIT at 3M.**

** An early termination visit will be completed if a patient or caregiver terminates participation in the study.**

** Final Intervention visit, Medical History, ECOG score, Concomitant Medications, and AUDIT will only be included in the Early Termination visit if the visit occurs prior to the 3M visit.**

** Baseline MELD can be within 6 weeks before the date of consent, but must be present prior to initial intervention visit.**

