## 11.2 Statistical Power

Based on the final site-specific enrolled counts (total n=936) and corresponding evaluable patient counts (as of September 30, 2024), there is 83.2% power (simulation based) for a superiority test to detect the originally specified MCID=9, with two sided type I error equal to 0.05, and utilizing SD=19.1, ICC= 0.09. The superiority hypothesis will be assessed first and only if such superiority is not demonstrated then the non-inferiority (NI) analysis will be performed. The NI margin is pre-specified. We chose the NI margin DELTA = 4. With this NI margin there is 79.2% power (simulation based) assuming presence of half of the considered superiority effect (MCID). The power values will be slightly higher when 3 months follow-up is completed resulting in few more patients with evaluable primary endpoint.

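### No liver-severity, performance-status, utilisation or same-visit symptom measure is pre-specified for the imputation model, which weakens MAR and may bias the contrast if missingness differs by arm

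*SAP*

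**What the plan says.** SAP 5.1 uses complete cases when at most 10% of patients lack the outcome, and multiple imputation above that. The imputation variables named there are the FACT-Hep total at baseline and months 1, 2 and 3, treatment, VA stratum and "baseline demographics (including age, gender, education level, employment status, marital status, and smoking status". SAP 12.4 assumes MAR. Besides every analysis-model variable, it brings in "additional auxiliary variables (including age, gender, education level, employment status, marital status, and smoking status) that may be predictive of the missingness". Those are the same six items.

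The trial also collects measures that neither section names:

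- Liver severity: MELD and CTP at baseline and month 3 (SAP 7 and 9; Protocol Table 2, row "MELD Labs (+/- 4 weeks for each time point) (Patients"), and HCC, which is a subgroup factor in SAP 6.
- Performance status: ECOG at the initial visit and months 1, 2 and 3 (SAP 9).
- Utilisation: hospitalisations and ER visits, from records and patient history (Protocol 9).
- Symptoms and distress: ESAS, PHQ-9 and the Distress Thermometer (DT) at baseline and months 1, 2 and 3 (Protocol Table 2).

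The timing matters. The Protocol synopsis says "ESAS, DT and PHQ-9 are conducted before the study visit (within 1 week of visit"), and places the other instruments, FACT-Hep among them, after the visit.

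**The concern.** MAR is credible only to the extent that the imputation model holds the variables that drive both missingness and the outcome. In a decompensated population, liver severity, performance status, recent admission and symptom load are more plausible drivers than marital or smoking status. That is a judgement; the documents report no predictors of missingness.

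Because of the visit timing, a patient can have month-3 ESAS, PHQ-9 and DT but no month-3 FACT-Hep. The named lists would leave those scores unused.

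If sicker patients are missing more often in one arm, their imputed scores come out too favourable and the contrast moves toward that arm. The same coefficient feeds the superiority test and the non-inferiority limit. If the arm concerned is Model 2, the error favours declaring non-inferiority.

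**Working it through.** **1. The plan's own precision.** Protocol 11.2 works "with two sided type I error equal to 0.05, and utilizing SD=19.1, ICC= 0.09", and reports "there is 83.2% power (simulation based) for a superiority test to detect the originally specified MCID=9" and "With this NI margin there is 79.2% power (simulation based) assuming presence of half of the considered superiority effect (MCID". Sites are 7 + 1 = 8 in Model 1 and 7 + 4 = 11 in Model 2 (SAP 2.1). Evaluable counts per site are not given, so equal site sizes m = N/19 are assumed:

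SE = 19.1 × √[(0.09 + 0.91/m)(1/8 + 1/11)]

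With N = 580, m = 30.5 and SE = 3.07. By normal approximation, superiority power is Φ(9/3.07 − 1.96) = 83.4% and non-inferiority power is Φ(8.5/3.07 − 1.96) = 79.0%, where 8.5 = 4.5 + 4. With N = 936 and a t reference on 17 df, the values are 82.7% and 78.3%. The stated 83.2% and 79.2% are reproduced to within a point either way. The SE is about 3.

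**2. Inputs for the bias check.** The documents give no figure for bias from the imputation model, so this is a large-sample regression-imputation calculation (800,000 simulated patients). It gives the expected imputed point estimate. Clustering is left out because only bias is sought.

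- From the documents: score SD 20.6 and SD of change 19.1 (SAP 2.3.1). If the SD is the same at both times, the baseline to month-3 correlation is 1 − 19.1²/(2 × 20.6²) = 1 − 364.8/848.7 = 0.57.
- Assumed: correlation 0.65 between months 1 and 2 and between months 2 and 3, and 0.57 for other pairs of visits.
- Assumed: a severity score correlated −ρ with month-3 FACT-Hep (ρ = 0.3 or 0.5), −0.8ρ with month 2, and −0.7ρ with baseline and month 1.
- Assumed: log-odds of missingness of 0.8 per SD of severity where dependence is present, and 15% to 35% missing.

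**3. Results.** Bias in the arm difference, in points; each range runs over ρ and the missing rates shown.

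| Missingness pattern | FACT-Hep at 0, 1, 2 months observed | Only baseline FACT-Hep observed | 0, 1, 2 months plus severity |
|---|---|---|---|
| Same dependence, same rate (15% or 25%) | about 0 | about 0 | about 0 |
| Same dependence, 15% vs 25% or 15% vs 35% | 0.15 to 0.54 | 0.23 to 0.84 | about 0 |
| Severity acts in one arm only, 15% to 35% missing | 0.26 to 0.97 | 0.39 to 1.52 | about 0 |
| Opposite dependence, 25% missing | 0.85 to 1.45 | 1.31 to 2.23 | about 0 |

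The opposite-dependence row is an extreme case, included as a bound.

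**4. Scale.** Against the margin of 4, 0.15 is 4%, 1.45 is 36% and 2.23 is 56%. Against an SE of 3.07 they are 0.05, 0.47 and 0.73 SE. Suppose the true difference sits at −4 and the bias favours Model 2. The chance of falsely declaring non-inferiority is then 1 − Φ(1.96 − bias/3.07), instead of 2.5%. That is 3.7% for a bias of 0.54 and 6.8% for 1.45. This uses the SE from step 1, without covariate adjustment or imputation variance.

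**5. What the auxiliaries cannot repair.** In a separate calculation missingness depended on current health itself (9% vs 20% missing; assumed score SD 21.35 and correlation 0.6, which again give 19.1 for change). Adding a same-visit symptom score correlated 0.5 to 0.8 with FACT-Hep cut the bias from 1.1–1.3 points to 0.6–1.1. It did not remove it.

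**The case against.** A reader might infer that the plan excludes severity and that the primary estimate is therefore biased. The documents do not support that.

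- Both lists are introduced by an including-type phrase, and the SAP 12.4 criterion (predictive of missingness) would admit MELD, CTP or ECOG. Treatment and stratum are named too.
- Nothing is imputed at or below 10% missing, and Protocol 11.3 expects few missing 3-month scores.
- The month-1 and month-2 FACT-Hep scores are already in the model. Of the 45 items, 18 concern disease-specific symptoms (Protocol 8), so part of the severity signal is present.
- Bias in the contrast also needs a difference between arms, and no missing rate by arm is given.
- A patient who misses the month-3 visit may lack the symptom scores as well.
- SAP 5.2 has two sensitivity analyses for deaths. SAP 5.3 adds diagnosis, comorbidity and possibly other baseline scores, with imputation if needed.

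All of this limits the size and certainty of the effect. It does not remove the gap. An open list lets auxiliaries be chosen after the data are seen, or not added at all. The death analyses leave survivors with missing scores untouched, and the supplementary model is not the primary one. Arm differences are possible: randomisation is by site, the delivery model is evident to site staff, and the three symptom scores go to Model 2 providers only (Protocol 5.2).

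A reader might also infer from step 1 that only about 570 to 590 patients are evaluable, so that imputation is certain. That does not follow. The match depends on equal site sizes and a normal reference, and non-evaluable patients include transplant and hospice exclusions and visits still pending.

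**Conclusion.** The gap in pre-specification is real, and it weakens the MAR assumption behind the primary imputation. Bias is possible but not shown. It requires more than 10% missing outcomes, severity information beyond the observed FACT-Hep scores, missingness that depends on severity, and a rate or dependence that differs by arm. If the arms are alike it is about 0. Otherwise it is roughly 0.15 to 1.5 points with interim scores observed and up to about 2.2 without them. These figures rest on assumed correlations, missing rates and log-odds. All lie below the margin of 4 and the MCID of 9, so they would matter mainly for a non-inferiority limit close to −4. This is a cheap improvement worth making, not a flaw that invalidates the analysis.

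**What to change.** In SAP 5.1 and 12.4, keep the variables already listed and add as pre-specified auxiliaries:

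- baseline MELD, CTP class and HCC;
- initial-visit ECOG;
- ESAS total, PHQ-9 and DT at baseline and months 1, 2 and 3;
- any hospital admission by month 3.

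These enter the imputation model only; the primary analysis model does not change. All are already collected, so the cost is SAP wording and a larger fully conditional specification model. Some auxiliaries will themselves be incomplete and must be imputed jointly, which calls for a convergence check. The change reduces bias where missingness depends on unobserved current health but does not remove it, and the SAP should say so.

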5.2 Primary Efficacy Sensitivity Analyses

Missingness of the primary outcome may also occur due to mortality prior to the 3 month follow-up. It is not likely mortality prior to the 3 month follow-up will bias treatment effect estimation because of randomization and we do not expect different survival due to treatment by that time. However, we will perform two sensitivity analyses. The first sensitivity analysis will be performed only if there are more than 10% of missing records and will utilize the mITT population but additionally exclude patients who died prior to the 3 month follow-up (MI will be utilized). The second sensitivity analysis will utilize the whole mITT population but we will set change in FACT-Hep total score (baseline to 3 months) for those who died prior to 3 months to the average of the 5% largest reductions in FACT-Hep total score among those alive by 3 months. MI will be utilized if there are more than 10% of missing records.

5.3 Primary Efficacy Supplementary Analysis

A supplementary analysis will involve multivariable analysis with the mixed linear regression model as in the primary analysis model but with inclusion of additional baseline covariates as fixed effects: age, sex, race, underlying diagnosis, comorbid conditions, any non-liver malignancy, and potentially other baseline scores. Multiple imputations will be used if needed.

5.4 Secondary Efficacy Analyses

The secondary endpoints will be presented as descriptive statistics by visit.

Where appropriate (i.e., change from baseline can be calculated), models similar to the primary endpoint superiority analysis may be utilized for secondary endpoint analyses.

The healthcare utilization endpoints will be analyzed as follows. For scheduled and unscheduled hospital admissions within 30 and 90 days of enrollment, proportions will be analyzed using random effects logistic regression. Counts of hospital admissions, ER visits, and unscheduled office visits over 1 year will be analyzed using Poisson regression with robust standard errors and non-identity dispersion via generalized estimating equations.

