3.5.2 Secondary Efficacy Endpoints

The endpoints inset below will be assessed as a change from baseline to 3 months (3-month score minus baseline score) in the mITT population:

- Overall quality of life (PROMIS-29, separate T scores)
- Symptom burden (modified ESAS, point score for each item, potentially total score for ESAS-r (9 components) and total score for the 13 components from this study)
- Depression severity (PHQ-9, total score)
- Distress (Distress Thermometer, total score)
- Satisfaction with care (FAMCARE-P, total score)
- Caregiver burden (ZBI-12, total score)
- Caregiver quality of life (PROMIS-29, separate T scores)
- Goal concordant care (Patient and Caregiver Questionnaire, total score)

Healthcare utilization in the mITT population:

- Proportion of patients with at least one scheduled or unscheduled hospital admissions within 30 days from the initial visit (based on data available from 1 month visit).
- Proportion of patients with at least one scheduled or unscheduled hospital admissions within 90 days from the initial visit (based on data available from 3 months visit).
- Rate of ER visits within 1 year from the initial visit.
- Rate of unscheduled office visits within 1 year from the initial visit.

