## 9. Data Collection

All instruments mentioned in section 8 above (Patient and Caregiver) will be completed at different time points, as outlined in Table 2. Survival data will be collected throughout the 12-month study period. Patient screening data collection will include: demographics (age, gender, and race), education level, and employment status. Patient baseline data collection will include MELD scores and CTP score. Initial visit data collection will include duration of liver disease, Charlson comorbidity index, current medications (collected throughout intervention visits and early termination visit if conducted prior to month 3), and history of psychiatric disease. In addition, we will capture the primary liver disease diagnosis and associated complications.

Caregiver screening data collection sheet will include: demographics (age, gender, and race), education level, employment status, duration of caregiving, and relationship with patient. Caregiver initial visit data collection will include any preexisting medical illness.

Health care utilization will be assessed using EMRs and patient history at each of the study visits (to include hospitalizations, ER visits). Liver transplantation and new onset of liver disease complications will be assessed throughout the study duration.

Billing codes are collected for each study intervention visit in both Models.

Please see Table 2 for more details on schedule of assessments. Please note that ESAS, DT and PHQ-9 will be conducted before the 1-, 2- and 3-month intervention visits, while all other assessments will be conducted after these study visits.

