## Protocol Version 4.0

hypothesis will be assessed first and only if such superiority is not demonstrated then the non-inferiority (NI) analysis will be performed. Non-inferiority (with the pre-specified NI margin  $\text{DELTA}=4$ ) will be claimed when  $L > -\text{DELTA}$ , where  $L$  is the lower limit of two-sided 95% confidence interval for the above- mentioned coefficient for the treatment indicator.

A *supplementary analysis* will involve multivariable analysis with covariate adjustment of the treatment effect performed with the mixed linear regression model as above but with inclusion of additional baseline covariates as fixed effects. The regression model will be evaluated with respect to functional form of continuous covariates and use splines if needed to accommodate non-linear effect of a covariate.

The secondary outcomes which are summarized by a score will be analyzed in fashion similar to the primary analysis described above. Survival will be summarized with Kaplan-Meier curves and Cox regression will be used for multivariable models, and will consider a shared-frailty model to account for center clustering.

For subgroup analyses, using multivariable models, a potentially differential impact of the intervention will be assessed across complementary subgroups by testing for interaction of the treatment variable with a subgrouping variable. In addition to tests we will present estimated treatment effects and the corresponding 95%CI for subgroup/subset treatment effects.

Palliative care knowledge gained by the hepatologists will be assessed by summarizing the responses to pre post assessment questionnaires in the training program.

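### SAP 5.4 names no covariates for the healthcare-utilisation models, although utilisation is scheduled for collection at baseline; precision may be lost on these secondary endpoints

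*SAP*

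**What the plan says.** SAP 5.4 treats utilisation in a separate paragraph. For admissions within 30 and 90 days, "proportions will be analyzed using random effects logistic regression". For the one-year endpoints, "Counts of hospital admissions, ER visits, and unscheduled office visits over 1 year will be analyzed using Poisson regression with robust standard errors", fitted by generalised estimating equations. Neither sentence lists a covariate. (The one-year admission count in that sentence is not among the endpoints in the SAP's Secondary Efficacy Endpoints section. The ER endpoint is: "Rate of ER visits within 1 year from the initial visit".)

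The baseline-adjusted form of the primary analysis does not reach these endpoints:

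- SAP 5.4: "Where appropriate (i.e., change from baseline can be calculated), models similar to the primary endpoint superiority analysis may be utilized". This is permissive and limited to change scores.
- Protocol 11.3: "The secondary outcomes which are summarized by a score will be analyzed in fashion similar to the primary analysis described above". Utilisation is not a score.
- SAP 5.1, on the primary model only: "We will also adjust for the baseline FACT-Hep total score and the binary randomization strata variable (VA vs. non-VA").

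On data, the "Healthcare Utilization" row of Protocol Table 2 is marked in all nine columns, Baseline included. Protocol 9 says: "Health care utilization will be assessed using EMRs and patient history at each of the study visits (to include hospitalizations, ER visits"). It does not name office visits, and neither place gives a look-back period.

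**The concern.** Use of hospital and emergency care tends to persist within a patient and to vary between centres. A patient's prior utilisation is therefore a natural covariate for later utilisation, as baseline FACT-Hep is for later FACT-Hep. The trial compares 8 consultative centres with 11 hepatologist-led centres, so the arms may start from different utilisation levels.

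The stratum matters too. Protocol 5.2 split the first 14 centres 4 VA against 3 VA by design, and the five added centres went 1 to Model 1 and 4 to Model 2. The VA share therefore differs between arms.

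At stake are the four utilisation hypotheses in Protocol 5.3: how precisely the arms are compared, and whether the covariates are fixed before the results are seen. SAP 12.6 applies no multiplicity adjustment, which makes an open covariate list less comfortable.

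**Working it through.** The plan states no power, event rate, ICC or baseline correlation for utilisation, so there is no figure to reproduce. SD 19.1, ICC 0.09 and power 83.2% belong to FACT-Hep change.

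**1. Layout.** Centres: 7 + 1 = 8 (Model 1) and 7 + 4 = 11 (Model 2), from SAP 2.1. Patients per centre: 936/19 = 49.3. VA centres: 8 in all, 7 of them among the first 14, so one was added later. The VA share is 4/8 v 4/11 or 5/8 v 3/11, depending on where that centre went.

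**2. Chance imbalance in a baseline measure, in patient SDs.**
SD = sqrt[(ICC + (1 − ICC)/49.3) × (1/8 + 1/11)].
Centre share of that variance = ICC / [ICC + (1 − ICC)/49.3].

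| Assumed ICC | SD of arm difference | Centre share |
|---|---|---|
| 0.02 | 0.093 | 50% |
| 0.05 | 0.122 | 72% |
| 0.09 | 0.153 | 83% |

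Half or more of the variance lies between centres. The shortcut that variance falls by rho squared therefore needs the centre-level correlation to equal rho as well as the patient-level one.

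**3. Gain for the count endpoints.** Poisson counts were simulated for 8 v 11 centres of 49 patients with no true effect, 400 runs per setting. Assumed: 6-month look-back, patient SD of log rate 0.8, and events per year, centre SD and correlation as shown. The ratio is the empirical variance of the log rate ratio with the patient's log(1 + baseline count) in the model, divided by the variance without it.

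| Correlation, baseline to follow-up | Events/year | Centre SD | Variance ratio |
|---|---|---|---|
| 0 | 1 | 0.3 | 1.00 |
| 0.3 | 1 | 0.3 | 0.96 |
| 0.5 | 1 | 0.3 | 0.91 |
| 0.5 | 0.5 | 0.3 | 0.96 |
| 0.7 | 1 | 0.2 | 0.84 |
| 0.7 | 1 | 0.3 | 0.80 |
| 0.7 | 1 | 0.5 | 0.75 |
| 0.7 | 2 | 0.3 | 0.74 |
| 0.7 patient, 0.9 centre | 1 | 0.3 | 0.75 |

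The variance is thus 0-9% lower at correlation 0.5 or below and 16-26% lower at 0.7. Adding the centre mean as a further term raised the variance ratio to 1.08 at correlation 0, so only the patient-level term is proposed.

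**4. Bias.** In the same runs the unadjusted log rate ratio averaged between −0.011 and 0.020, close to the true zero. The SD of the chance baseline log rate ratio between arms was 0.146 to 0.280, that is, ratios of exp(0.146) = 1.16 to exp(0.280) = 1.32 at one SD.

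**5. In power terms.** The starting powers are illustrative. With a noncentral t on 17 df, the noncentrality is divided by the square root of the variance ratio.

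| Variance ratio | From 80% | From 50% |
|---|---|---|
| 0.96 | 81.6% | 51.6% |
| 0.91 | 83.6% | 53.8% |
| 0.84 | 86.3% | 57.1% |
| 0.74 | 90.2% | 62.5% |

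**6. Other assumptions.** A set more favourable to adjustment (1.5 events a year, patient log-rate SD 1, centre SD 0.3-0.4, 3-6 month look-back) cut the variance by 17-42% at correlation 0.6-0.8 and by 6% at 0.4. For 90-day admission as yes/no, the cut was 2-17%. The 30-day endpoint was not simulated.

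**The case against.** - **Silence is not exclusion.** A reader might infer that the SAP decided against baseline adjustment here. It does not: SAP 5.4 leaves the whole covariate list open, stratum included. This objection stands, and the point is an unspecified list with a better choice available.
- **Chance imbalance is already in the interval.** A reader might infer that a baseline difference between arms would be taken for an effect of the care model. For chance imbalance the documents do not support this. The random effect and the robust standard errors carry between-centre variation into the interval, and the unadjusted estimate is centred correctly (step 4). What remains is lost precision and imbalance in the one realised allocation. Selection of patients after the centre's arm is known is a different matter. Protocol 14 lists it and plans to monitor it, and a prior-utilisation term would remove only part of it.
- **A large gain at moderate correlation.** A reader might apply the rho-squared rule and infer that 80% power becomes 90% at correlation 0.5. That needs the centre-level correlation to match, and a noisy baseline count shrinks the gain further. In step 3 a correlation of 0.5 takes 80% only to about 82-84%.
- **The baseline variable may be unusable.** Protocol 7 omits utilisation when it describes the baseline assessments, no look-back is defined, and office visits are not named in Protocol 9. This stands, and the fix is conditional on it.
- **Logistic models.** Adjustment changes the conditional odds ratio being estimated, so any benefit there is in power and need not be a narrower interval. This stands.

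**Conclusion.** The concern holds in limited form. SAP 5.4 specifies no covariates for the utilisation models, no other section supplies them, and Protocol Table 2 schedules the data from which a baseline covariate could be built. The planned analysis remains valid on average under chance imbalance.

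The cost for the count endpoints runs from nothing to about a quarter of the variance across the settings in step 3. It is 9% at most if prior and later utilisation correlate at 0.5 or below, and it becomes material at about 0.7. Every rate, correlation and variance component is assumed, and step 6 shows that the range moves with them. Gains for the yes/no admission endpoints are expected to be smaller. The missing VA stratum is part of the same gap and may matter as much, since the arms differ in VA share. Only secondary endpoints are involved.

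**What to change.** Amend SAP 5.4 before the utilisation data are analysed so that it lists the covariates of each utilisation model:

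- arm and VA stratum in all of them;
- log(1 + baseline admissions) in the admission models;
- log(1 + baseline ER visits) in the ER-visit model;
- for unscheduled office visits, the baseline count in the same form, only if it was captured.

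Make the baseline terms conditional on the baseline data having the same look-back in all centres. If they do not, record that in the SAP and keep arm and stratum. Report the model without the baseline term beside the adjusted one.

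The cost is SAP wording and one or two covariates per model. No new data collection is needed if the baseline entries are usable, but the look-back has to be checked first. The report should say that the adjusted odds ratio for admissions is conditional on prior utilisation.
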